6.7. Emergency Unblinding of Study Treatment

To maintain the integrity of the trial, emergency unblinding should occur only in exceptional circumstances when knowledge of the actual treatment is essential for further management of the subject. Investigators are encouraged to discuss with the Medical monitor if he/she believes that the unblinding is necessary.

If unblinding is deemed to be necessary, the investigator should follow the procedures for emergency unblinding as described in the Study Reference Manual (SRM).

The investigator is encouraged to maintain the blind as far as possible. The actual allocation must not be disclosed to the subject and/or other study personnel. Unblinding should not necessarily be a reason for study drug discontinuation.

7. TRIAL PROCEDURES

A detailed flowchart showing the assessments to be performed are in [Appendix G](#). Study days are defined as calendar days.

7.1. Consent

An oral explanation of the study covering its nature, purpose, risks and requirements will be given to the subject prior to any study-specific procedures being performed. Written information will also be provided to the subject in the appropriate language.

The subject will be given adequate time to consider their participation in the study and will be given the opportunity to ask the investigator about any aspect of the study. If participation is agreed, a Consent Form will be signed. If appropriate, a letter will be sent to the subject's primary care doctor informing him/her that the subject is to participate in the study.

Consent may be obtained at the Screening Visit, if appropriate. The informed consent form must be signed before any screening procedures are performed.

7.2. Visit 1: Screening Visit (up to Day -28)

The screening visit may be performed up to 28 days before first dose of investigational product.

The following assessments will be performed:

- Medical history, concomitant medications check
- Demography, gender
- Physical examination including 12-lead ECG, height and body weight
- Vital signs: sitting blood pressure (mmHG) after a 5-min rest, pulse rate and respiration rate
- Blood samples will be taken for the following assessments:
 - o virology: anti-HIV1&2, HBsAg, anti-HCV (see [Section 8.2.3](#))
 - o serum biochemistry (see [Section 8.2.3](#))
 - o hematology (see [Section 8.2.5](#))
 - o serum pregnancy test for all females of child-bearing potential
- Reserve blood samples will be taken (see [Section 7.9.1](#))
- A urine sample will be collected for urinalysis (see [Section 8.2.6](#)).

There will be a review of eligibility criteria. At the investigator's discretion, one or more screening laboratory tests may be repeated prior to Day 0 (Visit 2) and if not clinically significant and otherwise qualifying to determine eligibility.

For full details of sample collection, labeling, processing and storage for all laboratory tests please see the separate Laboratory Manual.

7.3. Visit 2: Baseline Visit (Day 0)

Dosing will take place within 28 days of the Screening Visit.

7.3.1. Before Dosing (Day 0)

The following procedures will be performed prior to dosing:

- Review of continued eligibility, including:
 - o elements of informed consent
 - o interim medical history
 - o concomitant medications
 - o Vital Signs
- Oral temperature. If the participant is febrile (oral temperature >38.0°C [100.4°F]) or has an acute illness, their enrollment must be re-scheduled. The decision to delay vaccinations because of a current or recent acute illness depends on the severity of the symptoms and their cause. Although a moderate or severe acute illness is sufficient reason to postpone vaccination, minor illnesses are not necessarily contraindications to vaccination. If re-scheduled, Day 0 must be within 28 days of all screening procedures; if greater than 28 days the subject must undergo a repeat screening visit. A new subject number will be assigned for repeat screening visits (see Study Reference Manual (SRM) for instructions on repeat screening).
- Body weight will be measured for reassessment of eligibility and calculation of the dose of HRIG in IU/kg
- A urine pregnancy test in females of childbearing potential
- A urine sample will be taken for urine hemosiderin (see [Section 8.2.7](#))
- Blood samples will be taken for the following assessments:
 - o rabies virus neutralizing antibodies (see [Section 8.1.4](#))
 - o markers of hemolysis (DCT, LDH, plasma free hemoglobin, serum haptoglobin and serum bilirubin) (see [Section 8.2.7](#))
- Reserve blood samples will be taken (see [Section 7.9.1](#))
- An archive serum sample will be taken (see [Section 7.9.2](#)) for long-term storage at -70°C for approximately 15 years.

The subject will then be randomized to treatment Group A or B, as described in [Section 6.2](#) .

7.3.2. Dosing on Day 0

Immediately prior to dosing, each injection site for the HRIG will be examined for pain, tenderness, erythema and induration (see [Section 8.2.2](#)) by the blinded site personnel, to establish a baseline for local tolerance.

According to the subject's randomized treatment, an IM injection of 20 IU/kg body weight BPL HRIG or HyperRAB® S/D will be administered. This will be followed by an IM injection of 1.0 ml licensed active rabies vaccine. Treatments for injection will be prepared and administered by unblinded site staff, who will remain separate to the study team as described in [Section 6.6](#).

The volume and location of administration of HRIG to each injection site will be recorded. The location of administration of active rabies vaccine, which must be a separate site to the HRIG injections, will also be recorded.

7.3.3. After Dosing

Study subjects will be observed in the clinic for a minimum of 30 minutes post-dose. Any adverse events will be assessed by the clinic staff and will be recorded in the subject notes.

At 30 minutes (\pm 5 minutes), all injection sites will be examined for pain, tenderness, erythema and induration by qualified clinical staff. (see [Section 8.2.2](#)).

7.4. Visits 3 to 7: Injections of Rabies Vaccine

The subject will return to the clinic on the following days:

Day 3 (Visit 3)

Day 7 (Visit 5)

Day 14 (Visit 6)

Day 28 \pm 2 days (Visit 7)

7.4.1. Before Dosing

The following assessments will be performed at all visits:

- Check for any new or changed adverse events and concomitant medications since the last visit
- Oral temperature. If the participant is febrile (oral temperature $>38.0^{\circ}\text{C}$ (100.4°F) or has an acute illness, active rabies vaccine must not be given. The subject may continue in the study but should receive no further doses of active rabies vaccine and will not be eligible for the per protocol population.

- Injection site assessment (only if symptoms were observed at the previous visit)
- Blood samples will be taken for rabies virus neutralizing antibodies (see [Section 8.1.4](#))

Reserve blood samples will be taken (see [Section 7.9.1](#))

In addition, the following assessments will be performed at the specified visits (see also the Schedule of Assessments in [Appendix G](#)):

- Vital signs: sitting blood pressure (mmHg) after a 5-min rest, pulse rate and respiration rate – Day 28 (see [Section 8.2.8](#))
- Blood samples will be collected for the following assessments:
 - markers of hemolysis (DCT, LDH, plasma free hemoglobin, serum haptoglobin and serum bilirubin) on Day 3. These tests including CBC may be repeated on Day 5, Day 7 and Day 14 depending on results obtained at the previous visit (see [Section 8.2.7](#)).
- A urine sample for hemosiderin – Day 3. This test may be repeated on Day 5, 7 and Day 14 depending on results obtained at the previous visit (see [Section 8.2.7](#)).

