7.4.2. Dosing of Active Rabies Vaccine

According to the subject's randomized treatment, an IM injection of 1.0 ml licensed active rabies vaccine will be administered. It may be administered to either the left or the right deltoid muscle, as long as there are no injection symptoms from previous HRIG or active rabies vaccine injections. The location of administration of active rabies vaccine will be recorded.

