7.4.3. After Dosing

Study subjects will be observed in the clinic for a minimum of 30 minutes post-dose. Any adverse events will be assessed by the clinic staff and will be recorded in the subject notes.

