8.2.2. Injection Site Observations

Each HRIG and vaccine injection site will be examined, and injection site observations will be assessed, pre-dose and 30 min [\pm 5 min] post-dose on Day 0 and at each subsequent clinic visit unless no symptoms are observed.

For injection site reaction (ISR) assessment criteria, refer to the table below:

Local Reaction to Injectable Product	Mild (Grade 1)	Moderate (Grade 2)	Severe (Grade 3)	Potentially Life Threatening (Grade 4)
Pain	Does not interfere with activity	Repeated use of non- narcotic pain reliever > 24 hours or interferes with activity	Any use of narcotic pain reliever or prevents daily activity	Emergency room (ER) visit or hospitalization
Tenderness	Mild discomfort to touch	Discomfort with movement	Significant discomfort at rest	ER visit or hospitalization
Erythema/Redness *	2.5 – 5 cm	5.1 – 10 cm	> 10 cm	Necrosis or exfoliative dermatitis
Induration/Swelling **	2.5 – 5 cm and does not interfere with activity	5.1 – 10 cm or interferes with activity	> 10 cm or prevents daily activity	Necrosis

* In addition to grading the measured local reaction at the greatest single diameter, the measurement should be recorded as a continuous variable.

** Induration/Swelling should be evaluated and graded using the functional scale as well as the actual measurement.

For the complete guidance (see Appendix A, Section 7): Toxicity Grading Scale for Healthy Adult and Adolescent Volunteers Enrolled in Preventive Vaccine Clinical Trials²⁵ :

All injection site reactions (ISR) will be recorded and graded on the ISR eCRF page. However, the investigator will determine if these are AEs. Injection site reactions will be recorded as AEs when the sign/symptoms require concomitant medications, or have an impact on the general condition of the subject as judged by the Investigator. The investigator will use their judgement to record the severity of the AE, using the appended toxicity scale to guide their assessment.

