10.6.2. Injection Site Observations

Injection site observations data will be summarized as appropriate.

Summary by Product

The number and percentage of subjects reporting injection site reactions will be summarized by preferred term and product (HRIG or vaccine).

Summary by Number of Injections

The number and percentage of subjects reporting injection site reactions will be summarized by preferred term, product (HRIG or vaccine) and number of injections.

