^h 2 samples will be collected at each timepoint, except for the Baseline Visit (Day 0) and the End-of-Study (EOS) Assessment (Day 140) at which 3 samples will be taken.

The additional plasma reserve samples will be taken in case viral nucleic acid testing is required to confirm viral serology results

ⁱ to be assessed at each subsequent visit until no symptoms are observed

^j bloods draw only **NO** vaccine at this visit

*archive serum sample-pre-dose, Day 0 and EOS, to be archive for approximately 15 years

^k routine hematology, chemistry or urinalysis can be repeated if clinically indicated or at the request of the medical monitor

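### Injection-site examination is unconditional only on Day 0, so late reactions and reactions to vaccine doses 2–5 are likely to be under-recorded

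*Protocol*

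**What the plan says.** On Day 0 the HRIG sites are examined before dosing (protocol 7.3.2; 8.2.2 adds the vaccine site). At 30 ± 5 minutes "all injection sites will be examined for pain, tenderness, erythema and induration by qualified clinical staff" (7.3.3). The grid in Appendix G marks only these two examinations.

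After Day 0 the rule appears in three wordings:

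- 7.4.1, for the vaccine visits on Days 3, 7, 14 and 28, before dosing: "Injection site assessment (only if symptoms were observed at the previous visit").
- 8.2.2: "and at each subsequent clinic visit unless no symptoms are observed".
- Footnote i of Appendix G, repeated in the SAP schedule: "to be assessed at each subsequent visit until no symptoms are observed".

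After vaccine doses 2–5, section 7.4.3 gives at least 30 minutes of observation and says "Any adverse events will be assessed by the clinic staff and will be recorded in the subject notes". It does not repeat the site examination found in 7.3.3. Sections 7.5 (Day 5), 7.6 (Day 49) and 7.7 (Day 140) list no site assessment.

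Section 8.2.2 sends every injection site reaction (ISR) to an ISR page of the eCRF, with a grade. It then sets a higher bar for adverse event status: "Injection site reactions will be recorded as AEs when the sign/symptoms require concomitant medications", or when they affect the subject's general condition. In the analysis (10.6.2), subjects with reactions "will be summarized by preferred term, product (HRIG or vaccine) and number of injections".

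**The concern.** Objective 4 is to compare safety and tolerability. Protocol 2.5 says that no clinical trial of the test product has been performed, and 2.6 says that robust trial data on the frequency of its undesirable effects are lacking. Local reactions are a listed class effect of HRIG (Table 3) and are among the most common reactions to the vaccine (2.8). The ISR table is thus one of the main tolerability results for a US licence application.

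As scheduled, that table would hold immediate reactions to the Day 0 injections, the persistence of those reactions, and whatever else subjects mention or staff happen to notice. A reader would take it as the reaction rate per product. Section 10.6.2 does not say how an unexamined site enters the percentage. If the denominator is all treated subjects, such a site counts as free of reaction. Late HRIG-site reactions matter most for the comparison, because the products differ and so do their injected volumes (6.6). The vaccine is the same in both arms, so missed vaccine reactions mainly distort the absolute profile.

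**Working it through.** The documents give no ISR rate and no detection rate, so there is no planned figure to reproduce. The check is a walk through the schedule.

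**Step 1. What follows each injection, by the visit sections of the protocol.**

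| Injection | Site examination listed later at the same visit | Next scheduled visit | Site examination listed there |
|---|---|---|---|
| HRIG and vaccine dose 1, Day 0 | Yes, 30 ± 5 min (7.3.3) | Day 3 | Only if symptoms at previous visit (7.4.1) |
| Dose 2, Day 3 | None (7.4.3) | Day 5 | None (7.5) |
| Dose 3, Day 7 | None (7.4.3) | Day 14 | Only if symptoms at previous visit |
| Dose 4, Day 14 | None (7.4.3) | Day 28 | Only if symptoms at previous visit |
| Dose 5, Day 28 | None (7.4.3) | Day 49 | None (7.6) |

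Doses without a listed post-dose site examination: 4 of 5, or 4/5 = 80%. This counts doses, not missed reactions.

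**Step 2. Does the trigger reset?** No wording says so. Under 7.4.1 or footnote i, a subject whose sites are clear at 30 minutes, and in whom no symptom is noted later, has no scheduled site examination through Day 140. There is a further snag at Day 7. The previous visit is then Day 5, where 7.5 schedules no site assessment on which the condition could rest.

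**Step 3. Do the wordings agree?** No. Section 7.4.1 looks back to the previous visit and covers only the vaccine visits. Footnote i stops once symptoms are absent and covers every later visit. Section 8.2.2 also covers every clinic visit, and could be read as an examination at each one with nothing to grade when the site is clear. On that reading it contradicts 7.4.1.

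**Step 4. Which reactions are exposed?** On the 8.2.2 scale, Grade 2 pain can be met by repeated use of a non-narcotic pain reliever, which also meets the medication criterion for an adverse event. Grade 1 pain does not interfere with activity. Erythema and induration are graded on a measured diameter (2.5–5 cm for Grade 1, 5.1–10 cm for Grade 2), which an interview cannot supply. The likely loss is mainly Grade 1, plus Grade 2 erythema or induration that qualifies on size alone.

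**Step 5. Effect on the comparison, on assumed inputs.** Let f be the share of subjects with a reaction who are recorded by any route, equal in both arms. The recorded difference is f × (p1 − p2). The recorded ratio is (f × p1)/(f × p2) = p1/p2. For assumed true rates of 40% and 30%:

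| f | Recorded rates | Difference | Ratio |
|---|---|---|---|
| 1 | 40% vs 30% | 10 points | 1.33 |
| 0.75 | 30% vs 22.5% | 7.5 points | 1.33 |
| 0.50 | 20% vs 15% | 5 points | 1.33 |
| 0.25 | 10% vs 7.5% | 2.5 points | 1.33 |

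Neither the rates nor f come from the documents. The table shows the direction and form of the effect, not its size in this trial.

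**The case against.** The strongest reply is that reactions can be captured without a scheduled examination:

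- Adverse events since the last visit are checked at every visit.
- Blinded staff interview subjects about reactions (6.6).
- Every dose is followed by at least 30 minutes of observation. A symptom seen then belongs to that visit, so it can trigger assessment at the next.
- Before doses 2–5 a deltoid may be used "as long as there are no injection symptoms from previous HRIG or active rabies vaccine injections" (7.4.2).
- Section 8.2.2 requires all reactions to be graded on the eCRF page, whether or not they are adverse events.

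All of this stands. A reader might infer from 7.4.1 that late reactions are never recorded, or that nearly all reactions to doses 2–5 are lost. The documents do not support either.

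These routes still leave a gap. Adverse event questioning is non-leading (Appendix A, section 3). Section 6.6 gives the interviews no timing, form or symptom list. The deltoid check asks for no grade and does not cover the thighs, where HRIG injections 1 and 2 go. The eCRF rule governs reactions that come to light; it schedules no examination.

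A second reply is that safety is compared descriptively, with no test (10.6), so no planned inference fails. That is correct, and it limits the point to the accuracy of the reported incidence and difference.

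**Conclusion.** The point holds in a limited form. Scheduled site examination is unconditional only on Day 0, the later rule is worded three ways, and none of the wordings restarts it after a new dose. Absolute ISR incidence is therefore likely to be underestimated, mainly for Grade 1 and some size-only Grade 2 reactions. By how much cannot be computed from the documents. The conclusion assumes that sites follow the visit sections as written and that the other routes capture mild reactions incompletely.

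A reader might also infer that the comparison between arms is biased in favour of one product. The documents do not support that. Both arms have the same rule, the same vaccine and blinded assessors, and nothing shows that capture differs by arm. With equal capture the absolute difference shrinks toward zero and the ratio is unchanged. A true difference in late HRIG-site reactions would be harder to see, but not necessarily invisible.

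**What to change.** Reconcile protocol 7.4.1, 8.2.2, Appendix G footnote i and the matching SAP footnote into one rule. In every subject, regardless of earlier symptoms, examine all HRIG and vaccine sites at the first scheduled visit after each injection and grade them on the ISR eCRF page. Add a direct question about site reactions since the last visit. Keep the rule of following up until symptoms are gone only for visits after that. List the examination in 7.5 and 7.6.

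The examinations would fall on Days 3, 5, 14, 28 and 49, which are 3, 2, 7, 14 and 21 days after the injections concerned. For doses 4 and 5 the direct question will therefore carry more weight than the examination, with some reliance on recall.

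The cost is protocol and SAP wording and a few minutes at visits that already exist, using existing staff and an existing eCRF page. The sample size does not change. The downside for the sponsor is that reported reaction rates will be higher.

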7.4.2. Dosing of Active Rabies Vaccine

According to the subject's randomized treatment, an IM injection of 1.0 ml licensed active rabies vaccine will be administered. It may be administered to either the left or the right deltoid muscle, as long as there are no injection symptoms from previous HRIG or active rabies vaccine injections. The location of administration of active rabies vaccine will be recorded.

7.4.3. After Dosing

Study subjects will be observed in the clinic for a minimum of 30 minutes post-dose. Any adverse events will be assessed by the clinic staff and will be recorded in the subject notes.

7.5. Visit 4: Day 5 PK sample

The subject will return to the clinic on Day 5. The following assessment will be performed:

- Check of any new or changed adverse events and concomitant medications since the last visit.
- Blood sample will be taken for rabies virus neutralizing antibodies (see [Section 8.1.4](#))
- Blood samples will be collected for markers of hemolysis (DCT, LDH, plasma free hemoglobin, serum haptoglobin and serum bilirubin), and CBC if the Day 3 DCT result was positive or missing (see [Section 8.2.7](#)).
- A urine sample for hemosiderin will be collected if the Day 3 DCT result was a positive or missing (see [Section 8.2.7](#)).

-
- Reserve blood samples will be taken (see [Section 7.9.1](#))

7.6. Visit 8: Day 49 PK sample

The subject will return to the clinic on Day 49 (\pm 4 days). The following assessments will be performed:

- Check of any new or changed adverse events and concomitant medications since the last visit
- Physical examination (see [Section 8.2.9](#))
- Vital signs: sitting blood pressure (mmHg) after a 5min rest, pulse rate and respiration rate (see [Section 8.2.8](#))
- Blood samples will be taken for the following assessments:
 - o rabies virus neutralizing antibodies (see [Section 8.1.4](#))
- Reserve blood samples will be taken (see [Section 7.9.1](#))

7.7. Visit 9: End-of-Study Assessment

An End-of-Study assessment will be conducted at Day 140 (\pm 7 days). The following assessments will be performed:

- Check of any new or changed adverse events and concomitant medications since the last visit
- Physical examination including 12-lead ECG and body weight
- Vital signs: sitting blood pressure (mmHg) after a 5 min rest, pulse rate and respiration rate (see [Section 8.2.8](#))
- Blood samples will be taken for the following assessments:
 - o hematology and serum biochemistry (see [Sections 8.2.4 and 8.2.5](#))
 - o Serum Pregnancy
 - o virology: anti-HIV1&2, HBsAg, anti-HCV (see [Section 8.2.3](#))
 - o rabies virus neutralizing antibodies (see [Section 8.1.4](#))
- Reserve blood samples will be taken (see [Section 7.9.1](#))
- A urine sample will be collected for urinalysis
- An archive serum sample will be taken (see [Section 7.9.2](#)) for long-term storage at -70°C or lower for 15 years.

7.8. Unscheduled Visits

Subjects will also attend the investigational site as required for collection of repeat blood samples.

7.9. Blood Sample Collection, Handling and Labeling

Full details on blood sampling collection, handling, storage and shipment of samples can be found in the Laboratory Manual.

7.9.1. Reserve Samples

Two reserve plasma/serum samples will be collected at all timepoints, for re-analysis if needed, e.g. if an original sample is spoiled or if results are discrepant. Additional reserve plasma samples will be taken pre-dose at Day 0 and Day 140 in case viral nucleic acid testing is required to confirm viral serology results (see [Section 8.2.3](#)). Human DNA testing will not be performed on any samples. Reserve samples will be stored at the study site at -70°C or lower for the duration of the study and sent to the central laboratory when requested by the sponsor (BPL). Reserve samples may be stored at a central laboratory archive until the license for BPL HRIG is granted in the US and EU (European Union) or other territories and will be used, if required, for repeat assays at the request of a regulatory agency.

